**Strengths:**

This is a pilot study. Study investigators have direct, inpatient access at Mayo Clinic Florida. The therapy department has adequate staffing levels to meet the demands of patient care for this study. A PubMed search found only a few published studies to date, demonstrating both safety and positive outcomes associated with using SCDs on hemiparetic UEs¹¹. Our study will examine further the benefit and use for a potentially more generalized usage. SCDs have been safely used for over 40 years on the LE's with very good outcomes regarding prevention of DVT in all patient populations and all age groups⁵. SCDs are safely used on patients with lymphedema on their UEs with good outcomes. Our study will only include cognitively intact patients as evidenced by BIMS score who will be able to sufficiently communicate tolerance of wearing an SCD. There will be no costs involved for this study.

Limitations:

Mayo Clinic currently utilizes the Kendall SCD™ 700 Series Compression Therapy Pump and leg sleeve which is not intended for UE use. Further, this system does not have an adjustable pressure setting, as this is set by the manufacturer. The Kendall SCD™ 700 Series is pre-set at a pressure of 45 mmHg¹. We believe this inability to adjust the pressure should not pose a problem. Extrapolating other SCD devices meant for the UE, 35-45 mmHg is a routine pressure for sustained pressure during UE lymphedema treatment and the Kendall SCD 700 series is pre-set at this level^{1,15}. Pressures up to 50 mmHg have been found safe for sustained usage¹⁵. This pressure is well tolerated when comparable devices were used on the UE. Similarly we feel the calf sleeve size is not necessarily a problem if the device is donned properly with adequate standard application (should be able to place 2 fingers between the SCD sleeve and the patient's arm²) and is monitored regularly. Further blood pressure cuffs are used for both UE and LE interchangeably with no adverse effect¹⁶.

Subject Information**Target accrual:**

Target sample size is 20 subjects.

Subject population (children, adults, groups):

Study population is adults, ages 18-100 years of age. Population to be studied includes patients admitted to MCJ, post-stroke with a hemiparetic upper extremity.

Inclusion Criteria:

Adults post stroke admitted to MCJ, with a weak upper extremity, or diminished sensation, which provide consent of participation by self-agreement. Patients with a weak or sensory impaired UE will be determined using the NIH Motor Arm subsection from the NIH scale and score a 1-4, dynamometry for hand grip strength or sensation deficits using the AISA C2-T2 standard points. Patients who have received thrombolytic therapeutic medicine > 13 hours (per site specific policy) will not be excluded from inclusion in this study. Patients who score > or = to 13 on the BIMS to ensure intact cognition.

Exclusion Criteria:

Inability to provide consent of participation; subjects with aphasia or the inability to effectively communicate their pain consistently or with questionable cognitive reliability scoring <13 on the BIMS (will be excluded), has an existing invasive line (PICC line, central venous catheter, AV fistula or AV graft); recent surgery or vein ligation in the involved extremity; recent skin graft in the involved extremity; confirmed DVT in the affected, upper extremity including axillary or subclavian veins; open or active wounds or infection in the involved extremity; upper extremity ischemia, gangrene, cellulitis or severe arteriosclerosis in the affected upper extremity; status-post axillary lymph node dissection on the involved side; congestive heart failure (CHF) acute exacerbation; acute edema of unknown etiology in the involved upper extremity; subjects with extreme deformity of the affected upper extremity; subjects with an acute kidney injury; subjects who are hemodynamically unstable^{1,7,17}; subjects under age 18 and over age 100; and patients who have received thrombolytic therapeutic medicine administered <13 hours (per site specific policy) prior to application of SCD sleeve. Women confirmed pregnant at the time of admission will be excluded.

Biospecimens

Collection of blood samples. When multiple groups are involved copy and paste the appropriate section below for example repeat section b when drawing blood from children and adults with cancer.

- a. **From healthy, non-pregnant, adult subjects who weigh at least 110 pounds.** For a minimal risk application, the amount of blood drawn from these subjects may not exceed 550ml in an 8-week period and collection may not occur more frequently than 2 times per week.

Volume per blood draw: _____ ml

Frequency of blood draw (e.g. single draw, time(s) per week, per year, etc.) _____

- b. **From other adults and children considering age, weight, and health of subject.** For a minimal risk application, the amount of blood drawn from these subjects may not exceed the lesser of 50 ml or 3 ml per kg in an 8-week period, and collection may not occur more frequently than 2 times per week.

Volume per blood draw: _____ ml

Frequency of blood draw (e.g. single draw, time(s) per week, per year, etc.) _____

Prospective collection of biological specimens other than blood: _____

Review of medical records, images, specimens

Check all that apply (data includes medical records, images, specimens).

Only data that exists before the IRB submission date will be collected.

Date Range for Specimens and/or Review of Medical Records:

Examples: *01/01/1999 through 12/31/2015*, or all records through *mm/dd/yyyy*.

Note: The Date Range must include the period for collection of baseline data, as well as follow-up data, if applicable.

The study involves data that exist at the time of IRB submission **and** data that will be generated after IRB submission. Include this activity in the Methods section.

Examples

- The study plans to conduct a retrospective chart review and ask subjects to complete a questionnaire.
- The study plans to include subjects previously diagnosed with a specific disease and add newly diagnosed subjects in the future.

The study will use data that have been collected under another IRB protocol. Include in the Methods section and enter the IRB number from which the research material will be obtained. *When appropriate, note when subjects have provided consent for future use of their data and/or specimens as described in this protocol.*

Enter one IRB number per line, add more lines as needed

Data Specimens Data & Specimens _____

Data Specimens Data & Specimens _____

Data Specimens Data & Specimens _____

Data Analysis

Power Statement:

The primary aim is use and tolerability which in twenty subjects should be adequately powered to eighty percent.

Data Analysis Plan:

The data will be largely descriptive around the aims in terms of age, gender, type of stroke, NIH stroke scale severity, weak upper extremity and other laboratory data from the electronic medical record retrospectively.

Endpoints:

Primary:

To establish that a leg sleeve and SCD can be used on a weak or sensory impaired UE post stroke and is tolerable to the patient 100% of the time.

Secondary:

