This will be a pilot study with an enrollment goal of 20 patients post stroke with a weak or sensory impaired UE. Mayo Clinic Florida received approximately 39 patients with stroke diagnosis per month according to records taken from January through October of 2019. Patients will be evaluated as routine standard part of care where standard chart review will be done and then patients will be screened for study inclusion for appropriateness for

participation in this study using the Brief Interview of Mental Status (BIMS) with scores $>$ or $=$ to 13 indicating intact cognition. If the patient does not score $>$ or $=$ to a 13 they will not be included in this study. If patient consent is obtained the patient will be enrolled in this study. Baseline data will be collected including pain, edema, nail bed color, sensation, skin integrity, grip strength and movement of the hemiparetic UE and photo taken prior to application of the sleeve and upon completion of 2nd check. The NIH score will be recorded as well at baseline. The patient's arm will be checked approximately every 2 hours following, for a total of approximately four hours recording pain, edema, nail bed color, sensation, skin integrity, movement, and patient tolerance during every check. Adverse effects attributable to sleeve usage will warrant removal of the SCD sleeve. These include, but are not limited to, compromised skin integrity, pain, patient intolerance, and increased edema or cyanosis. Subjects to which the SCD sleeve is removed will no longer be included in the study.

Application of LE SCD Sleeve:

Calf size LE SCD sleeve will be placed on the weak or sensory impaired UE below the cubital fossa and may include the hand if necessary. The patient's arm will be placed on a pillow providing support to the shoulder and arm keeping elbow extended. The sleeve will be applied with the standard approach/application to the calf when applied with adequate 2 finger spacing between the SCD sleeve and skin of the UE ². Patients will otherwise be allowed to move their arm as able freely while wearing the SCD sleeve.

Step -by –Step Schedule:

[figure not shown]
1. Order for PT or OT services received, OT and PT evaluations will be completed
2. PT/OT will screen during OT/PT evaluation process and perform standard protocol chart review for potential patient inclusion into this study and order will be obtained for inclusion by MD

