3. MD will place an order in the chart for the SCD and sleeve to be placed on the affected UE
4. Reason for SCD study and risks will be explained; and once all questions by patient are answered satisfactorily, informed consent will be signed by patient
5. Baseline skin and neurovascular assessment performed and documented by PT or OT prior to placement of SCD sleeve on patient (Picture of UE taken pre application and attached to chart):
 - a. Patient tolerance of wearing sleeve
 - b. Pain
 - c. Edema
 - d. Nail bed color
 - e. Skin integrity
 - f. Sensation
 - g. NIH Motor Arm subsection #5 score
 - h. BIMS score
 - i. NIH stroke scale score
 - j. Grip strength measure hand dynamometer
6. Measure circumference of affected forearm using tape measure to determine size of SCD sleeve
7. Placement of SCD sleeve on affected UE below cubital fossa, document patient initial tolerance and start time (T_1).
8. Subsequent UE checks to occur as follows, for a total of approximately four hours wearing time*:
 - 1st check – approximately 2 hours (h) after initial application (i.e. T_1).
 1. Take sleeve off patient, assess arm, obtain data (a.-g.), and document findings.

- 2nd check - approximately 2 hours (h) later (i.e. $T_1 + 2h = T_2$).
 1. Take sleeve off patient, assess arm, obtain data (a.-g.) and document findings (take post picture of UE and attach to chart).

* Any adverse effects, including patient tolerance, attributable to sleeve usage will warrant removal of SCD sleeve

Time (T)	T_i Baseline	T₁ 1st check	T₂ 2nd check
Patient tolerance “Are you tolerating this sleeve (Y/N)?”			
Pain (VAS)			
Edema (Girth)			
Nail bed color			
Skin integrity (Intact/Impaired)			
Sensation (Intact/Impaired)			
Motor Arm subsection of NIH			
Hand Dynamometer			
BIMS score			
NIH stroke scale score			

Subject Remuneration:

Subjects will not be provided a monetary incentive.

Sample Size:

The sample size of this pilot study will be 20 subjects. The average number of subjects when testing the use or effectiveness of a device is commonly between 10-40 subjects. This study is within the average range for this type of study.

Data Collection May Include:

1. Age
2. Gender
3. Race
4. Diagnosis
 - a. type of stroke
 - b. location of stroke
5. Vitals (reviewed and considered for inclusion criteria, not included in data collection chart)

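### Read literally, the protocol drops patients who do not tolerate the sleeve from the denominator of its 100% tolerability endpoint; the 80% power figure is also unsupported

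*Protocol*

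**What the plan says.** The primary endpoint (Data Analysis, Endpoints) is that the leg sleeve and pump can be used on the affected arm and that this "is tolerable to the patient 100% of the time". The protocol does not say whether the 100% refers to patients, to checks within a patient, or to wearing time.

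The Study Design or Overview section says that adverse effects attributable to the sleeve warrant its removal, and lists them: "These include, but are not limited to, compromised skin integrity, pain, patient intolerance, and increased edema or cyanosis". The next sentence reads: "Subjects to which the SCD sleeve is removed will no longer be included in the study".

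The Step-by-Step Schedule has a parallel footnote: "Any adverse effects, including patient tolerance, attributable to sleeve usage will warrant removal of SCD sleeve". It says nothing about leaving the study. The same schedule takes the sleeve off every patient at each of the two checks ("Take sleeve off patient, assess arm, obtain data") and records tolerance as a yes/no answer.

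On size, the Power Statement says: "The primary aim is use and tolerability which in twenty subjects should be adequately powered to eighty percent". The Data Analysis Plan that follows says: "The data will be largely descriptive around the aims". The Sample Size section justifies 20 only by a customary range of 10 to 40 subjects for device studies.

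**The concern.** Intolerance is both the failure event of the primary endpoint and a reason for no longer being included in the study. If the second rule governs the count, the event that should lower the percentage instead removes the patient from it, and the endpoint can hardly fail. If it does not govern the count, the reader still cannot tell which patients the percentage covers, because no counting rule for removed patients is stated.

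This matters because later work is meant to build on the result. Aim 2 looks to new practice standards, and the Background says that studies of benefit can follow once use of the sleeve is established. A 100% obtained by dropping failures would misinform those steps.

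The power sentence adds an assurance that nothing in the protocol backs. This is the lesser matter, since the choice of 20 rests on custom and not on that sentence.

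**Working it through.** **1. The plan's own figure: 80% power with 20 patients.**

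Inputs in the protocol: n = 20, one group, yes/no tolerance, a 100% target. Not in the protocol: null rate, expected rate, alpha, sidedness, test, success rule. The 80% therefore cannot be reproduced. To see whether it could be right, I assumed an exact single-arm binomial test at a nominal one-sided 5%, with the cut r as the smallest count for which P(X ≥ r | n = 20, null) ≤ 0.05:

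| Assumed null | Cut r | Attained size | True rate giving 80% power |
|---|---|---|---|
| 50% | 15 | 2.1% | 79.9% |
| 60% | 17 | 1.6% | 88.3% |
| 70% | 18 | 3.55% | 92.2% |
| 80% | 20 | 1.15% | 98.9% |
| 90% | none | – | – |

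At a 90% null no valid rule exists, because even 20/20 has probability 0.90^20 = 12.2%. If success means 20 of 20, 80% power needs p^20 = 0.80, so p = 0.80^(1/20) = 0.989. The figure can thus be reached under some assumed inputs and not under others, and the protocol names none of them.

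**2. The denominator.**

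Let k of 20 patients have the sleeve removed for intolerance, and let the rest tolerate it. The values of k are assumptions.

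- Kept as failures: (20 − k)/20.
- Dropped: (20 − k)/(20 − k) = 100% for every k below 20.

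Exact (Clopper–Pearson) 95% limits for x of n: the lower is the 2.5% quantile of Beta(x, n − x + 1), and the upper is the 97.5% quantile of Beta(x + 1, n − x). When x = n the lower limit is 0.025^(1/n) and the upper is 1.

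| k | Kept in denominator | Dropped |
|---|---|---|
| 0 | 20/20 = 100% (83.2–100%) | 20/20 = 100% (83.2–100%) |
| 1 | 19/20 = 95.0% (75.1–99.9%) | 19/19 = 100% (82.4–100%) |
| 2 | 18/20 = 90.0% (68.3–98.8%) | 18/18 = 100% (81.5–100%) |
| 3 | 17/20 = 85.0% (62.1–96.8%) | 17/17 = 100% (80.5–100%) |

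In practice the literal reading gives a result close to 100% and not necessarily equal to it. A patient who answers no at the last check, when the sleeve comes off anyway, might still be counted.

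**3. How often the rule would matter.**

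The chance of at least one such removal among 20 is 1 − p^20. The protocol gives no expected p, so a range is shown:

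- p = 99%: 18%
- p = 98%: 33%
- p = 95%: 64%
- p = 90%: 88%

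**The case against.** The strongest reply is that the sentence describes conduct and not analysis. It stands in the design overview, directly after the rule for taking the sleeve off, and the Data Analysis section states no exclusion from the primary endpoint. The target of 20 is an enrolment goal, and no passage provides for replacing patients. Tolerance is recorded as yes or no at each check, which suggests that a no is meant to be captured. Because the sleeve also comes off every patient at each check, the sentence cannot be meant in its barest literal sense and is loosely worded. All of this stands, and it makes the milder reading plausible. It does not settle the count: nowhere does the protocol say that a removed patient counts as not tolerating, and the only statement on their inclusion points the other way.

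A second reply is that a pilot needs no power calculation and that null rate, alpha and test belong in an analysis plan, which may exist but is not shown. That is fair, and it is why the power half is minor. But the protocol itself asserts a power figure, beside an analysis it calls largely descriptive. An analysis plan that kept removed patients would also have to depart from the literal wording of the protocol.

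A third reply is that few removals are likely, since the Background and Limitations expect comparable pressures to be well tolerated. At an assumed 99% tolerability, no removal occurs in about 82% of such studies (0.99^20 = 0.818), and the rule then changes nothing. That also stands. The effect depends on a rate that the protocol does not state.

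**Conclusion.** The point holds. As written, the protocol can be followed in a way that removes failures of the primary endpoint from its own denominator, and it contains no rule that prevents this. With one assumed removal, the result moves from 95.0% to 100%, and the lower 95% limit from 75.1% to 82.4%. The gap widens with each further removal.

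A reader might infer that the protocol definitely excludes these patients and guarantees 100%. The documents do not support that: the wording also admits that only participation stops. What is established is a literal reading that biases the result and the absence of any counting rule that would correct it.

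A reader might also infer that the 80% is wrong or that 20 patients are too few. Neither follows. Some assumed inputs give 80% at n = 20, so the figure is unsupported and not shown to be miscalculated.

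The removal counts, null rates, one-sided 5% level and true tolerability rates above are assumptions. The confidence limits depend only on the counts and n.

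**What to change.** 1. **Endpoint.** Define it as the proportion of all patients who had the sleeve applied who tolerate it at every check through about four hours, with an exact 95% confidence interval. The sponsor may keep 100% as a target on this denominator.
2. **Inclusion sentence in Study Design or Overview.** Reword it so that patients whose sleeve is removed stay in the analysis, and removal for intolerance or an attributable adverse effect counts as not tolerating. Report early removals for unrelated reasons separately. This concerns counting only: when the sleeve is removed, and what observation follows, are left unchanged. The schedule footnote makes no statement about inclusion and needs no edit.
3. **Power Statement.** Replace it with precision: with 20 patients, 20/20, 19/20 or 18/20 tolerating gives exact 95% confidence intervals of 83.2–100%, 75.1–99.9% and 68.3–98.8%.

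The cost is a few sentences of protocol text and a recorded reason for each early removal. Sample size and checks do not change. The drawback for the sponsor is that the stated assurance becomes less favourable and an observed 100% becomes harder to report.
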